4.1.1 Analysis junctures

The analyses for this study will occur at three junctures as described in section 1.2.1. The endpoints analyzed at each juncture will be as follows:

- For primary analysis of the lead-in phase: Primary endpoint of percent change in testosterone; PSA responses at 4 and 12 weeks; incidence of treatment emergent adverse events with emphasis on feminizing side effects.
- For primary analysis of the randomized phase: Primary endpoint of percent change in testosterone; PSA responses at 4 and 12 weeks; other sex hormone changes at 4 and 12 weeks; components of fat and glucose metabolism at 4 and 12 weeks; incidence of treatment emergent adverse events with emphasis on feminizing side effects.
- Final analysis: Separate analyses will be performed for the lead-in phase and the randomized phase of the study. For the lead-in phase, summaries for visits after 12 weeks will be presented for testosterone, PSA, and safety endpoints. For the randomized phase, summaries at the visits after week 12 will be presented for testosterone, sex hormones, components of fat and glucose metabolism, and additional efficacy and safety endpoints.

4.1.2 Handling missing data

All missing or partial data will be presented in the participant data listing as they are recorded on the Case Report Form. Except as noted, missing data will not be estimated or carried forward in any statistical analysis.

When appropriate, the following rules will be implemented so as not to exclude participants from statistical analyses due to missing or incomplete data:

Incomplete death dates:

Every effort should be made to resolve incomplete or missing dates during the course of the study (i.e., edit checks, data cleaning/monitoring etc.). However, in rare circumstances, missing parts of either the censoring date or the event date may occur where an imputation algorithm must be defined. In general, the following rule should be followed: A missing month or year is not acceptable. To impute a value for day, day 15 of the month will be used for the calculation.

ARAMON V3.0 Page: 13 of 31

Partial or missing AE dates:

Refer to Appendix 1: Imputation rule for partial missing dates for the imputation rule for incomplete AE dates.

Laboratory Assessments:

To facilitate the transformation of the data, the least detectable values of Testosterone and other laboratory values will be used when the baseline data notes a less than detectable value. When such a value is not uniformly available across sites, then the lowest value of the laboratory analyte across participants at baseline in the data cut will be used.

FACT-P Questionnaire:

For FACT-P, total scores and subscale scores (physical well-being, social/family well-being emotional well-being, and functional well-being) will be assessed. Where there are missing items, subscale scores will be prorated if >50% of items on subscale are completed. This will be done by multiplying the sum of the subscale by the number of items in the subscale, then dividing it by the number of items answered. If \leq 50% of the items are answered for any domain, then the score of that domain will be set to missing (see scoring of FACT-P in Appendix 2: Scoring procedures for FACT-P). The total score will be set to missing if the related overall item response rate is less than or equal to 80% (without prorated subscale items). In addition, a total score will only be calculated if all the component subscales have valid scores.

The statistical evaluation will be performed by using the software SAS (release 9.4 or higher; SAS Institute Inc., Cary, NC, USA. All data will be presented in the participant data listing as they are recorded on the Case Report Form (CRF), i.e., partially missing data will appear as such.

4.1.3 Data rules

In case of repeated measurements over multiple dates per time point,

- For baseline, the nearest visit (scheduled or unscheduled) to the start of the study drug administration will be used;
- For post-baseline measures, the scheduled visit will be used. Unscheduled visits will be used if there are no scheduled visits then the first unscheduled visit will be used.

If there are repeated measurements per time point on the same day (e.g., laboratory values, vital signs, etc.),

- For baseline, the latest measurement will be used;
- at any post baseline time point, the first measurement at the visit will be used.

4.2. Primary Endpoint Analysis

The primary endpoint, percent change in testosterone, is defined in Section 1.1. The primary endpoint for both phases will be analyzed using a natural logarithm transformation consistent with sample size assessments in Section 5 given a distribution for the endpoint which is skewed right. Further, the percent change endpoint is a re-scaled fold change from baseline statistic for which such a transformation is often conducted. The mean fold change and

ARAMON V3.0 Page: 14 of 31

percent change estimates are interpretable as geometric means given the logarithmic transformation.

The primary endpoint will be analyzed in the evaluable population.

4.2.1 Main Analytical Approach

The primary endpoint for the lead-in phase will be analyzed at 12 weeks after start of darolutamide for the last participant in the lead-in phase. If the study continues into the randomized phase, the primary endpoint analysis for the randomized phase will be conducted 12 weeks after start of study treatment for the last participant in the randomized phase.

4.2.1.1 Lead-in Phase

The participant testosterone levels at baseline and week 12 will be transformed to natural logarithm values. The mean and 95% Confidence Interval of the differences between the week 12 and baseline values will be computed and back transformed by exponentiation to obtain the mean fold change M_F with its 95% Confidence Interval [L_F , U_F]. The mean percent change Δ can be obtained as $\Delta = 100*(M_F-1)$ with Confidence Interval [$100*(L_F-1)$, $100*(U_F-1)$]. In addition to the estimated mean percent change and its confidence interval, summary statistics will include the mean fold change with confidence intervals, and the mean, standard deviation, median, quartiles, minimum, and maximum of percent change computed from the raw week 12 and baseline testosterone values.

4.2.1.2 Randomized Phase

The participant level differences between the natural log transformed testosterone values at week 12 and baseline will be computed. These differences will be compared across the darolutamide and enzalutamide arms using a two-sample t-test. SAS code will be similar to code shown in Appendix 4: Randomized phase primary endpoint analysis for natural logarithm transformed Testosterone. Two-sided p-values from this t-test will be reported to assess whether the null hypothesis can be rejected in favor of the alternate hypothesis described in Section 2. Additionally, the estimated difference between darolutamide and enzalutamide and the 95% confidence limits from the t-test will be back transformed by exponentiation to obtain the ratio of the fold change in testosterone values from baseline for darolutamide to that for enzalutamide and the confidence limits for this estimate. Within treatment group, mean percent change and confidence intervals as well as other summary statistics described for the lead-in phase will also be reported.

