4.1 Overall Design

This is a two-stage open label phase 2 study with a lead-in single-arm phase and the randomized phase, to assess the impact of ARI darolutamide or enzalutamide as a monotherapy treatment on serum testosterone levels in men with hormone-naïve prostate cancer experiencing biochemical recurrence (BCR) after failure of treatment with curative intent for localized prostate cancer. Secondary endpoints to be evaluated include the impact of ARI monotherapy on energy metabolism and the metabolism of sex hormones as well as PSA response and safety. Exploratory endpoints will evaluate changes in bone metabolism, physical function, and quality of life profiles. The study design is shown in the Figure 4-1.

In the lead-in phase, approximately 25 participants will be treated with darolutamide for 52 weeks. The primary endpoint analysis of the lead-in phase will occur when all participants in the lead-in phase have been on treatment for 12 weeks, unless the participant discontinued due to lost to follow-up, withdrawal, or death. The secondary endpoint analysis of lead-in phase (see Table 3-1) will occur after patients have been treated for 52 weeks.

[figure not shown]
The study team will review the findings form the lead-in phase of the study, to provide input on interpretation of the results from the lead-in phase which will help guide a decision on the conduct or not of the randomized phase as well as potential changes in the study design for the randomized phase by the Sponsor. In any case, the conduct of the randomized phase is conditional on obtaining a mean percent change in serum testosterone from baseline for the darolutamide arm of less than 45%. Additional non-binding thresholds to help with the decision on the conduct of, or changes in the randomized phase, are that the incidence of feminizing side effects observed is below than that previously reported

Depending on the results of the evaluation and in case of the decision to proceed with the randomized phase, the primary endpoint may be modified, and the statistical assumptions revised. The Sponsor withholds the right to conduct or stop the lead-in phase or start the randomized phase in case data on testosterone levels from patients treated with darolutamide alone would become available from other ongoing studies.

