5.1 Inclusion Criteria

- 1. Male of \geq 18 years of age.
- 2. Patients must have histologically or cytologically confirmed adenocarcinoma of the prostate.
- 3. Prior treatment with primary radical prostatectomy or definitive RT for localized prostate cancer.
- 4. Patients must have PSA ≥0.2 ng/mL after ART or SRT post-RP or after RP in participants who are unfit for ART or SRT, OR PSA ≥2 ng/mL above the nadir after primary RT only. (RP, radical prostatectomy; ART, adjuvant radiotherapy; SRT, salvage radiotherapy; RT primary radiotherapy)
- 5. The presence of < 5 asymptomatic (symptomatic lesions should be excluded) metastatic lesions (except for visceral metastases), and including extra-pelvic lymph nodes, and > 2 cm pelvic lymph nodes, on conventional or PSMA-PET based imaging methods is permitted. Lesions that need treatment with any opioid based analgetic are considered symptomatic.
- 6. PSADT ≤ 20 months calculated per PCWG3 + RECIST 1.1 per Scher et al. (Scher et al. 2016) and MSKCC nomogram.
- 7. ECOG PS of 0 1.
- 8. Serum testosterone >150 ng/dl.
- 9. Patients must have adequate organ function within 4 weeks before the first dose of study intervention and evidenced by:
 - a. Absolute Neutrophil Count $\geq 1500/\text{mm}^3$
 - b. Platelet count > 100,000/mm³
 - c. Total bilirubin < 1.5 x ULN
 - d. ALT and AST $\leq 1.5 \text{ x ULN}$
 - e. Creatinine < 2.0 X ULN
 - f. Creatinine clearance (CrCl) of ≥ 30 mL/min. CrCl should be calculated at screening using the Cockcroft-Gault formula: Creatinine clearance for males (mL/min) = (140 age in years) x (body weight in kg)/[72 x (serum creatinine in mg/dl)].
 - g. PTT, PT, INR \leq 1.5 x ULN (except if on the aprentic anticoagulation in which case the patient can be enrolled if stable and anti-coagulation levels are appropriate for their condition per good clinical practice).

NOTE: All values must be obtained within 4 weeks prior to first dose of darolutamide.

NOTE: Participants must not have received any growth factor within 4 weeks or a blood transfusion within 7 days prior to the hematology laboratory sample obtained at Screening.

- 10. Sexually active male participants must agree to use condoms as an effective barrier method and refrain from sperm donation, and/or their female partners of reproductive potential to use a method of effective birth control, during the treatment with study intervention and for 3 months after treatment with study intervention.

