2.1. Multiplicity Adjustment

Not applicable as there are no co-primary endpoints or interim analyses requiring special means for the control of the overall false positive error rate.

ARAMON V3.0 Page: 11 of 31

3. Analysis Sets

For purposes of analysis, the following populations are defined:

Table 3-1: Populations for analyses: Lead-in phase

Population	Description
Screened	All participants who sign the informed consent form
Evaluable	All enrolled participants having testosterone data at baseline and Week 12. Enrolled participants include those who signed informed consent and met all inclusion and none of the exclusion criteria.
Safety	All enrolled participants who received any darolutamide post-enrollment regardless of their eligibility for the study.

Table 3-2: Populations for analyses: Randomized Phase

Population	Description
Screened	All participants who sign the informed consent form
Evaluable	All randomized participants having testosterone data at baseline and week 12 who signed informed consent and met all inclusion and none of the exclusion criteria.
Safety	All randomized participants who received any quantity of study intervention, regardless of their eligibility for the study. The safety evaluation will be performed based on the intervention actually received.

Final decisions regarding the assignment of participants to analysis sets will be made during the review of study data and documented in the final list of important deviations, validity findings and assignment to analysis set(s).

ARAMON V3.0 Page: 12 of 31

4. Statistical Analyses

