4.8. Changes to Protocol-planned Analyses

There are no changes to the analyses described in the protocol.

ARAMON V3.0 Page: 20 of 31

5. Sample Size Determination

The sample sizes corresponding to the planned analysis methodology are provided below.

Lead-in Phase

Approximately 25 participants will be assigned to darolutamide to achieve at least 20 evaluable participants. This sample size will help estimate the mean percent change in serum testosterone level at 12 weeks with a 95% confidence interval having a half-width of no more than 25%, assuming a true mean percent increase of less than 45% and a standard deviation of 65%. This assessment uses a log normal distribution for percent change.

Randomized Phase

Contingent on the results of the evaluation in Section 1.2.1, the randomized phase statistical assumptions may be revised, or the study could be terminated after lead-in.

Should the study continue to the Randomized phase unmodified, a maximum of 40 participants (20 per arm) will be randomly assigned to study treatment (darolutamide or enzalutamide) such that approximately 34 evaluable participants complete the study. The randomized stage will require a sample size of 20 per group to provide 85% power to test the null hypothesis of no difference between groups on mean percent change at the two-sided 0.05 level. This assessment is based on a mean percent change in Testosterone from baseline and Standard Deviation for the Darolutamide arm of 45% and 65% versus 110% and 75% respectively for Enzalutamide and assumes a log normal distribution for percent change.

ARAMON V3.0 Page: 21 of 31

6. Supporting Documentation

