| 16 | 35.9 | 1.9 | | | |
| 17 | 36.8 | 1.9 | | | |
| 18 | 37.6 | 1.9 | | | |
| 19 | 38.5 | 1.9 | | | |
| 20 | 39.3 | 1.9 | | | |
| 21 | 40.2 | 1.9 | | | |
| 22 | 41.2 | 1.9 | | | |
| 23 | 42.1 | 1.9 | | | |
| 24 | 43.2 | 2.0 | | | |
| 25 | 44.3 | 2.0 | | | |
| 26 | 45.6 | 2.2 | | | |
| 27 | 47.1 | 2.3 | | | |
| 28 | 48.9 | 2.7 | | | |
| 29 | 51.3 | 3.0 | | | |
| 30 | 59.0 | 6.2 | | | |
| *SE = Standar | d Error on T-sco | re metric | | | |

PROMIS Physical Function 6b form

PROMIS Fatigue 8a form

ARAMON V3.0 Page: 27 of 31

Appendix 4: Randomized phase primary endpoint analysis for natural logarithm transformed Testosterone

Following data structure will be obtained for the Input dataset LN_DATA. LN_Change will be the difference between the LN(Testosterone) values at Visit 12 from the LN value at baseline.

```
Subjid trt LN_Change
Daro 0.5
Daro 0.9
ENZA 0.5
ENZA 0.8
```

The following SAS code will be used for the two-sample t-test.

```
PROC TTEST DATA=LN_DATA SIDES=2 ALPHA=0.05 H0=0;
CLASS TRT;
VAR LN_CHANGE;
RUN:
```

Appendix 5: Lead-in phase analysis for natural logarithm transformed Testosterone and other endpoints using the log transformation

For the primary end point analysis, PROC TTEST procedure similar to Appendix 4: Randomized phase primary endpoint analysis for natural logarithm transformed Testosterone will be used without the CLASS statement.

For the lead-in phase, the following data structure will be obtained for the input dataset LN_DATA to Proc Mixed. LN_Change will be the difference between the LN(Testosterone) values at Visit from the LN value at baseline. During the lead-in phase there will be no enzalutamide data.

```
Subjid trt
           visit LN Change
          WK2 0.5
     Daro
     Daro WK4 0.9
     Daro
          WK8 1.3
     Daro
          WK16 1.6
          WK24 1.7
     Daro
     Daro WK36 1.7
     Daro
          Wk52 1.6
     Daro
          WK2 0.4
     Daro WK4 1.3
```

Following PROC Mixed code will be used.

```
PROC MIXED DATA = LN_DATA;
CLASS VISIT SUBJID;
```

ARAMON V3.0 Page: 28 of 31

```
MODEL LN_CHANGE = VISIT /DDFM = KR;
RANDOM SUBJID;
REPEATED / TYPE = TOEP SUBJECT=SUBJID;
LSMEANS VISIT/ CL;
RUN;
```

Then the estimate for VISITS WK24 and WK52 will be retained. The dataset will have 2 lines. The fold change pair for each fold change (FC) can be computed as:

```
FC = EXP(Estimate);

LCL_FC = EXP(Estimate - StdErr*quantile('T', .975, DF));

UCL_FC = EXP(Estimate + StdErr*quantile('T', .975, DF));
```

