These fold changes can be converted to Percent Change as:

```
PC = (FC-1)*100;

LCL_PC = (LCL_FC -1)*100;

UCL_PC = (UCL_FC -1)*100;
```

Similar code will be used for the other endpoints using the same transformation.

Appendix 6: Randomized phase analysis for natural logarithm transformed Testosterone and other endpoints using the log transformation

The following data structure will be obtained for the input dataset LN_DATA to Proc Mixed. LN_Change will be the difference between the LN(Testosterone) values at Visit from the LN value at baseline.

```
Subjid trt
                LN Change
          visit
     Daro WK2 0.5
     Daro
          WK4 0.9
     Daro WK8 1.3
     Daro WK16 1.6
     Daro WK24 1.7
     Daro WK36 1.7
          Wk52 1.6
     Daro
     Daro WK2 0.4
     Daro WK4 1.3
     ENZA WK2 0.5
     ENZA WK4 2.2
     ENZA WK8 2.6
     ENZA WK16 2.8
```

The following PROC Mixed code will be used.

ARAMON V3.0 Page: 29 of 31

```
PROC MIXED DATA = LN_DATA;
CLASS TRT VISIT SUBJID;
MODEL LN_CHANGE = TRT|VISIT /DDFM = KR;
RANDOM SUBJID(TRT);
REPEATED / TYPE = TOEP SUBJID(TRT);
LSMEANS TRT*VISIT/ DIFF SLICE = VISIT;
RUN;
```

Output the dataset created by LSMEANS. The data will be of the form:

| Obs | Effect | Trt | Visit | _Trt | _Visit | Estimate | StdErr | DF | t-value F | Probt |
|-----|-----------|------|-------|------|--------|----------|--------|-----|-----------|-------|
| 1 | TRT*VISIT | Daro | WK2 | Daro | WK4 | 0.4 | 0.3 | XXX | XXX | 0.xx |
| 2 | TRT*VISIT | Daro | WK2 | Daro | WK8 | 0.8 | 0.32 | XXX | XXX | 0.xx |
| | | | | | | | | | | |
| | TRT*VISIT | Daro | WK2 | ENZA | WK2 | -0.2 | 0.31 | XXX | xxx | 0.xx |
| | | | | | | | | | | |
| | TRT*VISIT | Daro | WK52 | ENZA | WK52 | 0.4 | 0.3 | XXX | XXX | 0.xx |

From this dataset the records where 'Trt NE _Trt', where Trt = 'Daro', where 'Visit = _Visit' and Visit IN ('WK24','WK52") will be selected. This will select the two records where we are reporting results per the secondary objective. The fold change ratio (FCR) and the lower (LCL) and upper (UCL) confidence intervals for the fold change ratio will be obtained as:

```
FCR = EXP(Estimate);

LCL_FCR = EXP(Estimate - StdErr*quantile('T', .975, DF));

UCL_FCR = EXP(Estimate + StdErr*quantile('T', .975, DF))));
```

For fold change (FC) within treatment, the PROC MIXED will be repeated above with the following LSMEANS statement:

LSMEANS TRT*VISIT/CL;

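### The primary randomized comparison uses baseline testosterone only by subtraction; ANCOVA on log baseline would cost at most about 1.4 points of power and could gain several times that if the slope is well below 1

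*SAP*

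**What the plan says.** SAP 4.2.1.2 defines the response as a change score: "The participant level differences between the natural log transformed testosterone values at week 12 and baseline will be computed". The comparison follows: "These differences will be compared across the darolutamide and enzalutamide arms using a two-sample t-test". Protocol 9.4.1.2 says the same. SAP Appendix 4 ("The following SAS code will be used for the two-sample t-test") gives code with treatment as the only classification variable and log change as the only response.

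The repeated-measures model for later visits in SAP Appendix 6 is "MODEL LN_CHANGE = TRT|VISIT /DDFM = KR", again without a baseline term. Neither document plans a baseline-adjusted sensitivity analysis for testosterone.

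Three other passages matter here:

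- SAP Table 3-2 limits the randomized evaluable set to "All randomized participants having testosterone data at baseline and week 12", plus consent and eligibility. The covariate would therefore be complete by definition.
- SAP section 5 gives the planning values as "Darolutamide arm of 45% and 65% versus 110% and 75% respectively for Enzalutamide", with a log-normal distribution and about 34 evaluable patients out of 40.
- Protocol 4.1 says that, after the lead-in, "the primary endpoint may be modified, and the statistical assumptions revised".

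**The concern.** A change score is one particular baseline adjustment, with the regression slope of log week-12 on log baseline set to 1 rather than estimated. If the true slope is below 1, a fraction (1 − slope) of any chance baseline imbalance stays in the estimated ratio of fold changes, and variance that could be removed remains in the error term. ANCOVA estimates the slope, for one degree of freedom and a small penalty for estimating it.

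With about 34 evaluable patients, precision is limited, and under one reading of the planning means power is already below the stated 85%. What is at stake is the width of the confidence interval and power. Validity is not in question.

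**Working it through.** **Inputs from the documents.** Mean percent change (SD) is 45% (65%) for darolutamide and 110% (75%) for enzalutamide. The test is two-sided at 0.05, with 20 per arm randomized and 34 evaluable, so 17 per arm.

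**Assumed inputs.** The documents give neither the slope nor the log-baseline SD. I use slopes of 0.5–1.0 and log-baseline SDs of 0.25–0.45. The eligibility floor ("Serum testosterone >150 ng/dl", Protocol 5.1) trims the low tail, which is why SDs down to 0.25 are shown.

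**Log scale.** The log variance is ln(1 + (SD/mean fold)²).

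- Darolutamide: ln(1 + (65/145)²) = 0.183, SD 0.428.
- Enzalutamide: ln(1 + (75/210)²) = 0.120, SD 0.346.
- Mean variance 0.1516, pooled SD 0.389.

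The log difference depends on how the planning means are read:

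- Reading A (geometric means): ln(2.10/1.45) = 0.370.
- Reading B (arithmetic means): subtract half of each log variance from the log mean, giving 0.370 + (0.183 − 0.120)/2 = 0.402.

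**The plan's own figure.** n per arm = (1.960 + 1.036)² × (0.183 + 0.120) / difference². Reading A gives 19.8, so 20 per arm. Reading B gives 16.9, so 17 per arm, or 34 evaluable. The stated design reproduces. With the noncentral t distribution, power is 83.4% (A) or 88.9% (B) at 20 per arm, and 76.7% (A) or 83.1% (B) at 17 per arm.

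**ANCOVA.** Residual variance = 0.1516 − (1 − slope)² × (baseline SD)², multiplied by 1 + 1/30 for the estimated covariate, with 31 df instead of 32. Example at slope 0.5 and SD 0.45: (0.1516 − 0.25 × 0.2025) × 1.033 = 0.104. The standard error relative to the t-test is √(0.104/0.1516) = 0.83.

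Results at 17 per arm; ranges run over baseline SD 0.25 to 0.45:

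| True slope | SE relative to t-test | ANCOVA power, A (t-test 76.7%) | ANCOVA power, B (t-test 83.1%) |
|---|---|---|---|
| 0.5 | 0.96–0.83 | 79.7–89.9% | 85.7–94.0% |
| 0.6 | 0.98–0.90 | 78.1–84.6% | 84.3–89.9% |
| 0.7 | 1.00–0.95 | 76.8–80.4% | 83.2–86.4% |
| 0.8 | 1.01–0.99 | 76.0–77.5% | 82.4–83.8% |
| 0.9 | 1.01 | 75.4–75.8% | 82.0–82.3% |
| 1.0 | 1.017 | 75.3% | 81.8% |

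The slope at which power is equal is 0.71, 0.79 and 0.84 for baseline SDs of 0.25, 0.35 and 0.45, under both readings. At SD 0.20 it falls to about 0.64.

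**Simulation.** At slope 0.5, SD 0.35 and reading A, 20,000 simulated trials gave 76.7% against 84.0%. Other settings agreed with the formula within about 1 point. Type I error was near 5% for both methods.

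**Imbalance.** The SE of the baseline difference is SD × √(2/17), or 0.086–0.154. A one-SE imbalance (exceeded in about 32% of trials) moves the unadjusted ratio by exp((1 − slope) × SE) − 1. That is 4.4–8.0% at slope 0.5, 2.6–4.7% at 0.7, 1.7–3.1% at 0.8, and 0 at slope 1.

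**What the plan's SD implies.** Week-12 log variance = 0.1516 + (2 × slope − 1) × (baseline SD)². A slope of 1 would require the log SD at week 12 to exceed that at baseline by 85%, 50% or 32% (baseline SD 0.25, 0.35, 0.45). Break-even requires about 69%, 35% or 20%. The t-test is therefore the better choice only if log-scale spread widens appreciably on treatment.

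**The case against.** The strongest case against is that nothing is wrong. The t-test on log change is valid and matches the hypothesis and the sample-size basis, and the proposed gain rests on two quantities the documents do not give. That stands, and it limits how hard the point can be pressed.

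The size can also be flattered. The 13-point gain is one corner (slope 0.5, SD 0.45, reading A: 89.9 − 76.7 = 13.2); reading B gives 10.9 there. Weighting slopes 0.5 to 1.0 equally, the average gain under reading A is only 0.2 points at SD 0.25, 1.8 at SD 0.35 and 3.9 at SD 0.45, and it is a loss of 0.4 at SD 0.20. The eligibility floor points towards smaller SDs. A material gain is possible but not established.

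The imbalance shifts are not a separate harm. Under randomization the t-test's standard error already covers them, so they restate the precision loss for a single trial.

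Calibration from the lead-in is weak. With 20 patients and a slope near 0.5, the slope's standard error would be about 0.2–0.4. All those patients receive darolutamide, so the enzalutamide slope is not informed, and the figures above assume a common slope.

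None of this removes the asymmetry: the loss is bounded near 1.4 points and the possible gain is several times that. Room for exploratory analyses (Protocol 9.4) is not pre-specification.

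**Conclusion.** The point holds as an efficiency improvement that should be made; it is not an error in the plan. At 17 evaluable per arm, ANCOVA loses 1.3–1.4 points of power if the slope is exactly 1 and is about level at 0.8. It gains 2.6–13.2 points at a slope of 0.5. The range 0.71–0.84 is where the methods break even, so a useful gain needs a slope clearly below it: about 0.5 at SD 0.30, or 0.6–0.65 at SD 0.40, for 4 points or more.

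Confidence is medium, because the slope and baseline SD are assumed. The estimand is unchanged: ANCOVA still targets the ratio of fold changes, and the null hypothesis stands. No size was worked out for the Appendix 6 model or for FACT-P. The SAP 4.3.1.2 text on FACT-P gives no code and leaves baseline handling open, and the conclusion does not rely on it.

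**What to change.** Before any randomized data are seen:

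- Pre-specify as primary an ANCOVA of log week-12 testosterone on treatment with log baseline testosterone as covariate. Using log change as the response gives the same treatment estimate.
- Report the back-transformed adjusted ratio with its 95% CI. Give within-arm fold changes as adjusted means too, so that they divide to the reported ratio.
- Keep the planned t-test as a sensitivity analysis.
- For consistency, add log baseline and its interaction with visit to the Appendix 6 model.
- Use the lead-in data to inform the baseline SD and, loosely, the slope. Do not choose between models on the randomized data.

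The cost is one covariate and one degree of freedom, with revised text in Protocol 9.4.1.2, SAP 4.2.1.2 and SAP Appendix 4. SAP 4.8, which now declares no departures from the protocol, must stay consistent with the amended protocol. No new data are needed. If the sponsor prefers not to change the primary test, a pre-specified ANCOVA sensitivity analysis is the lesser alternative.
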